### **FPT155+pembrolizumab**

FPT155 will be administered once every 3 weeks (Q3W) over approximately 60 minutes by intravenous IV infusion followed by 200 mg of pembrolizumab administered by intravenous (IV) infusion after the completion of FPT155. Eligible patients with advanced non-small cell lung cancer will be enrolled.

Combination dose escalation will start with a FPT155 dose that is a minimum of two dose levels lower than the highest dose cleared in FPT155 monotherapy.

Combination dose exploration will include up to 30 patients who may be enrolled at one or more dose levels to further evaluate safety, PK, PD, and clinical activity (conditional upon the dose level clearing dose escalation criteria).

For patients enrolled for treatment with FPT155 and pembrolizumab, treatment will be administered Q3W until disease progression, unacceptable toxicity or consent withdrawal; if one study drug is discontinued, the other may be continued for up to an additional 12 months.

#### **4.1.1.1 Cohort Review Committee**

Safety will be monitored throughout the study by the Sponsor's CRC, comprised of, but not limited to, Phase 1a study investigators, the Sponsor's medical monitor, and the Sponsor's safety representative. The CRC will meet routinely to review the emerging safety, PK, PD, and efficacy data, and to make dose escalation decisions. The CRC may recommend further

evaluation of the safety at a given dose. The CRC will also review cumulative safety data in order to identify safety concerns that may emerge due to cumulative exposure beyond the DLT window. The process for dose escalation decisions, dose interval recommendations, and the roles and responsibilities of the CRC will be detailed in the CRC Charter.

#### 4.1.1.2 Proposed FPT155 Dose Levels

FPT155 will be initially administered Q3W, on Day 1 of each 21-day cycle.

The anticipated dose levels are outlined in [Table 5](#).

**Table 5: Anticipated Dose Levels**

Design	Dose	Regimen
Accelerated titration design	0.07 mg FPT155	Q3W
	0.21 mg FPT155	Q3W
	0.70 mg FPT155	Q3W
	2.1 mg FPT155	Q3W
3+3 design	7 mg FPT155	Q3W
	21 mg FPT155	Q3W
	42 mg FPT155	Q3W
	70 mg FPT155	Q3W
	140 mg FPT155	Q3W
	280 mg FPT155	Q3W
	560 mg FPT155	Q3W
	840 mg FPT155	Q3W
	1260 mg FPT155	Q3W

Abbreviations: Q3W = once every 3 weeks.

Planned dosing increments take into account conservative estimates of RO and PA through both CD28 and CTLA-4. Fixed 3-fold escalation increments are proposed while projected engagement of CD28 is low; more conservative increments (2-fold or less) are proposed at higher CD28 occupancy levels.

The Sponsor may add cohorts with alternative dose levels or dose regimens (e.g., different dosing frequency, intermediate dose levels) upon review of safety, PK, and PD profiles to achieve optimal target exposure with acceptable tolerability. The dose level of 700mg was replaced by 840mg based on preliminary PK showing dose-proportional increases in exposure and approximately 30-50% interpatient variability in exposure at a given dose level – the range of exposures from FPT155 560mg and from FPT155 700mg (25% increase in dose) were predicted not to be significantly different. A 1.5-fold increment in dose levels has been selected

above 560mg based on early safety results showing an absence of DLTs or cytokine release syndrome through the 560mg dose level with the presence of immune-related toxicity manageable with standard of care treatment for irAEs. Following clearance of a dose at the Q3W schedule, more frequent (eg Q2W) dosing at the same dose level may be evaluated using the 3+3 framework.

#### 4.1.1.3 Dose Limiting Toxicity Definitions

The DLT evaluation interval begins on the first day of treatment upon start of infusion and continues for 21 days. Patients who receive at least 1 dose of study treatment and remain on study for the 21-day DLT evaluation interval or patients who discontinue study treatment for drug-related AEs before clearing the 21-day DLT evaluation interval will be considered evaluable for DLT determination.

DLTs during Phase 1a dose escalation are defined as any of the following deemed by the investigator as related to FPT155:

- Absolute neutrophil count (ANC)  $< 1.0 \times 10^9/L$  for  $> 5$  days duration or Grade 3 febrile neutropenia (eg, ANC  $< 1.0 \times 10^9/L$  with a single temperature of  $> 38.3^{\circ}C$  or fever  $> 38^{\circ}C$  for more than 1 hour)
- Platelets  $< 25 \times 10^9/L$  or platelets  $< 50 \times 10^9/L$  with clinically significant hemorrhage
- Aspartate aminotransferase (AST) or ALT  $> 3 \times$  upper limit of normal (ULN) with concomitant total bilirubin  $> 2 \times$  ULN not related to liver involvement with cancer
- Grade 3-4 non-hematological toxicity except:
  - Grade 3 fatigue  $< 7$  days
  - Grade 3 nausea and Grade 3-4 vomiting and diarrhea lasting  $< 72$  hours in patients who have not received optimal anti-emetic and/or anti-diarrheal therapy
  - Grade 3 endocrinopathy that is adequately treated by hormone replacement
  - Laboratory value that may be corrected through replacement within 48 hours
- Grade 2 neurological toxicity except headache and peripheral neuropathy in patients with Grade 1-2 peripheral neuropathy at entry

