**Dose Limiting Toxicity Definitions:**

The DLT evaluation interval begins on the first day of treatment upon start of infusion and continues for 21 days. Patients who receive at least 1 dose of study treatment and remain on study for the 21-day DLT evaluation interval or patients who discontinue study treatment for drug-related AEs before clearing the 21-day DLT evaluation interval will be considered evaluable for DLT determination.

DLTs during Phase 1a dose escalation are defined as any of the following deemed by the investigator as related to FPT155:

- Absolute neutrophil count (ANC)  $< 1.0 \times 10^9/L$  for  $> 5$  days duration or Grade 3 febrile neutropenia (eg, ANC  $< 1.0 \times 10^9/L$  with a single temperature of  $> 38.3^{\circ}C$  or fever  $> 38^{\circ}C$  for more than 1 hour)
- Platelets  $< 25 \times 10^9/L$  or platelets  $< 50 \times 10^9/L$  with clinically significant hemorrhage
- Aspartate aminotransferase (AST) or alanine aminotransferase (ALT)  $> 3 \times$  upper limit of normal (ULN) with concomitant total bilirubin  $> 2 \times$  ULN not related to liver involvement with cancer
- Grade 3-4 non-hematological toxicity except:
  - Grade 3 fatigue  $< 7$  days
  - Grade 3 nausea and Grade 3-4 vomiting and diarrhea lasting  $< 72$  hours in patients who have not received optimal anti-emetic and/or anti-diarrheal therapy
  - Grade 3 endocrinopathy that is adequately treated by hormone replacement
  - Laboratory value that may be corrected through replacement within 48 hours
- Grade 2 neurological toxicity except headache and peripheral neuropathy in patients with Grade 1-2 peripheral neuropathy at entry

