#### Additional DLT Considerations for FPT155 in combination with pembrolizumab

Because pembrolizumab is a known immune checkpoint inhibitor and one of the proposed mechanisms of action of FPT155 is immune checkpoint blockade, immune-related adverse events (irAEs) are anticipated with this combination. An irAE is defined as a clinically significant AE that is associated with study drug exposure, without a clear alternate cause, and consistent with an immune-mediated mechanism. Based on that background, the first occurrence of the following irAEs will not be considered a DLT because they may occur with immune therapy and are likely to be fully reversible per [Appendix 8](#):

- Grade 3 tumor flare (defined as local pain, irritation, or rash localized at sites of known or suspected tumor)
- Grade 3 non-skin immune-related adverse event (irAE) that resolve to a Grade 1 or less within 14 days with management per [Appendix 8](#)
- Transient (resolving within 6 hours of onset) Grade 3 infusion-related AEs
- Grade 3 drug-related bronchospasm or anaphylactic or anaphylactoid reactions

Dose escalation may be paused prior to determining an MTD based on observed safety, tolerability, or emerging PK or PD results.

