#### 4.2 Study Treatment and Duration

FPT155 will be administered Q3W over approximately 60 minutes by IV infusion.

In combination with FPT155 and pembrolizumab, pembrolizumab will be administered a minimum of 30 minutes following completion of the FPT155 infusion. Pembrolizumab should be administered per the pembrolizumab Product Information.

Treatment is administered Q3W until disease progression, unacceptable toxicity, or patient withdrawal. If one drug is discontinued, treatment may continue with the other alone for up to an additional 12 months. Treatment beyond disease progression may be allowed in patients with initial RECIST v1.1 defined progressive disease if the criteria in Section 4.3 are met.

Patients should have end of treatment (EOT) follow-up visits approximately 28 days and 100 days after the last dose of treatment on study. In addition, patients enrolled in dose expansion will be followed for survival.

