### **6.9.6 Dose Interruptions During Study Treatment Administration**

#### **6.9.6.1 FPT155**

Infusion of FPT155 must be stopped if any AE  $\geq$  Grade 3 occurs during the infusion.

If bronchospasm or dyspnea occurs in a patient during the infusion, the infusion must be stopped.

In addition, at the investigator's discretion, the infusion rate for FPT155 may be reduced or stopped if a less severe AE (Grade 1 or 2) occurs during the infusion. If a Grade 3 or less severe AE resolves within 4 hours, the infusion may be restarted at half the previous rate and promptly managed according to the discretion of the Investigator. If the same AE appears again with the same severity at any time during the restarted infusion, the infusion should be discontinued, and no further dosing of FPT155 will occur without consultation with the Sponsor or Sponsor's designee.

If a patient experiences an infusion reaction prior to completion of the infusion, the infusion must be stopped, and the patient should be promptly managed and monitored according to signs and symptoms, and local clinical protocol until there is a complete resolution of the event.

Symptoms of infusion reactions may include: fever, chills, rigors, urticaria, hypotension and hypertension with headache, wheeze, breathlessness, hypoxia, and pulmonary infiltrates. For patients whose infusion-associated events were either Grade 1 or 2, and completely resolved on the day of the infusion, the infusion may be resumed at the discretion of the Investigator at a slower rate with premedication. All subsequent infusions for that patient should then be administered at the reduced rate of infusion with pre-medications. Pre-medications may include medications such as corticosteroids, diphenhydramine, acetaminophen and/or bronchodilators as indicated. FPT155 will be permanently discontinued for patients who have experienced Grade 3 (lasting longer than 4 hours) or above infusion -associated AEs, and for patients who have recurrent infusion-associated reactions after restarting the infusion despite pre-medications and slower infusion.

If a patient experiences an infusion reaction, the patient's vital signs (temperature, blood pressure, pulse, and respiration rate) should be monitored during the infusion, as well as every 30 minutes after the infusion for a minimum of 2 hours and until resolution of the infusion reaction.

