### 7.4 Replacement of Patients

Patients in Phase 1a dose escalation will be replaced if they are unevaluable for DLT (refer to Section 4.1.1.3).

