### 9.3 Populations for Analyses

The following analysis populations are defined for the study as follows:

Population	Description
Enrolled	All patients who sign informed consent and are registered as enrolled in IVRS/IWRS.
Efficacy Population	All patients who have received any portion of at least one dose of study drug.
DLT-Evaluable Population	All patients enrolled into Phase 1a dose escalation portion of the study who received at least 1 dose of all assigned study drug(s) and remain on study for the 21-day DLT evaluation, or who experienced a DLT before clearing the 21-day DLT evaluation interval.
Safety Population	All patients who have received any portion of at least one dose of any study drug.
Response-Evaluable Population	All patients who met eligibility criteria, received at least one dose of any study drug, have measurable tumor lesions at baseline, and have at least one post-baseline disease assessment unless the death and clinical progressive disease occurred prior to the first post baseline disease assessment.
PK-Evaluable Population	All patients who have received at least one dose of study drug and have had sufficient PK sample for the calculation of at least one PK parameter on at least one Study Day.

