4.3 DLT-Evaluable Population

All patients enrolled into Phase 1a dose escalation portion of the study who received at least 1 dose of all assigned study drug(s) and remain on study for the 21-day DLT evaluation period, or who experienced a DLT before clearing the 21-day DLT evaluation interval.

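### The DLT-evaluability rule that governs escalation and replacement differs from the one used to report DLT incidence, so a combination dose may be cleared partly on a patient who never received pembrolizumab

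*Protocol*

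**What the plan says.** **Escalation and replacement.** Protocol 4.1.1.3, repeated in the Synopsis, gives two routes to being evaluable. The first covers "Patients who receive at least 1 dose of study treatment and remain on study for the 21-day DLT evaluation interval". The second says that "patients who discontinue study treatment for drug-related AEs before clearing the 21-day DLT evaluation interval will be considered evaluable for DLT determination". Section 7.4 provides that escalation patients "will be replaced if they are unevaluable for DLT" and refers back to 4.1.1.3.

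**Reporting.** Protocol 9.3 admits escalation patients who "received at least 1 dose of all assigned study drug(s) and remain on study for the 21-day DLT evaluation, or who experienced a DLT" within the window. SAP 4.3 does the same: patients who "received at least 1 dose of all assigned study drug(s) and remain on study for the 21-day DLT evaluation period", or who had a DLT before the interval ended. Protocol 9.4.2 and SAP 6.3.1.7 summarise DLTs on this population. DLT incidence is a primary endpoint for the combination (Protocol 3.0).

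**Combination dosing.** FPT155 is infused first. Under Protocol 4.2, "pembrolizumab will be administered a minimum of 30 minutes following completion of the FPT155 infusion". Section 6.9.6.1 requires the FPT155 infusion to stop for any event of Grade 3 or higher, and adds that "FPT155 will be permanently discontinued for patients who have experienced Grade 3 (lasting longer than 4 hours) or above" infusion-associated events. The combination part of 4.1.1.3 removes certain first occurrences from the DLT definition. These include "Transient (resolving within 6 hours of onset) Grade 3 infusion-related AEs" and Grade 3 bronchospasm or anaphylactic reactions, the latter with no time limit.

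**Clearing a dose.** Table 6, which also governs the combination (Section 4.1.4), clears a dose at 0/3 or 1/6.

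**The concern.** The two rules classify some patients differently, and neither document reconciles them. The second route in 4.1.1.3 can be met by a patient who had no DLT and did not receive every assigned drug. Such a patient fills a place in the 3+3 cohort as a non-DLT and is not replaced. Under 9.3 and SAP 4.3 the same patient is not evaluable.

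This matters most in the combination, where the cohort exists to observe the two drugs together. A dose could be cleared with fewer than three, or fewer than six, patients exposed to both. The DLT table in the study report would then show a denominator that Table 6 does not recognise and that differs from the one used to escalate.

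**Working it through.** **1. One patient under both rules.** Take a combination patient with a first Grade 3 infusion reaction to FPT155 that lasts more than 4 hours and resolves within 6.

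| Step | Source | Result |
|---|---|---|
| Infusion stopped, FPT155 ended for good | 6.9.6.1 | Required |
| Is it a DLT? | 4.1.1.3, combination exemptions | No |
| Pembrolizumab not given, all treatment stopped | Investigator's choice | Permitted, not required |
| Evaluable for escalation? | 4.1.1.3, second route | Yes, as a non-DLT |
| Replaced? | 7.4, by reference to 4.1.1.3 | No |
| In the reported DLT population? | 9.3, SAP 4.3 | No: not all assigned drugs, no DLT |

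**2. Denominators.** Escalation would use 0/3 or 1/6; the report would show 0/2 or 1/5. Exact one-sided 95% upper limits for the DLT rate (the 95th percentile of a Beta distribution with parameters x+1 and n−x) are:
- 0/3: 63.2%; 0/2: 77.6%
- 1/6: 58.2%; 1/5: 65.7%

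**3. Chance of clearing a dose.** The plan gives no operating characteristics for its 3+3, so there is no stated figure to reproduce. The only input from the plan is the Table 6 rule. The DLT rates below are assumptions.

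With true DLT rate p and q = 1 − p, P(clear) = q³ + 3pq² × q³. At p = 0.25: 0.4219 + 0.4219 × 0.4219 = 0.600.

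Now let one of the first three patients have DLT probability kp, where k = 1 is full risk and k = 0 is none:

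P(clear) = q²(1 − kp) + [2pq(1 − kp) + q²kp] × q³

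At p = 0.25 and k = 0: 0.5625 + 0.375 × 0.4219 = 0.721.

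| Assumed p | k = 1 | k = 0.5 | k = 0 |
|---|---|---|---|
| 0.10 | 0.906 | 0.924 | 0.941 |
| 0.25 | 0.600 | 0.660 | 0.721 |
| 0.30 | 0.494 | 0.564 | 0.634 |

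The k = 0 column is an upper bound, because the patient has had some FPT155 and is observed afterwards. Over assumed rates of 10% to 60%, the largest k = 0 increase is 15.4 points, at 40% (0.309 to 0.464).

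**4. Allowing for how often it happens.** Suppose each combination patient is such a case with probability r (assumed) and then carries no DLT risk. The effective rate is p′ = p(1 − r), entered in the first formula with p = 0.25:
- r = 1%: p′ = 0.2475, P(clear) = 0.605, up 0.5 points
- r = 2%: p′ = 0.2450, P(clear) = 0.611, up 1.1 points
- r = 5%: p′ = 0.2375, P(clear) = 0.627, up 2.7 points

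These too are upper bounds.

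**The case against.** **The rules do not generate this patient by themselves.** A reader might infer from 6.9.6.1 and the exemptions that they do. The documents do not support that. Section 6.9.6.1 ends FPT155 only. Section 4.2 lets the other drug continue alone and sets a minimum gap before pembrolizumab but no maximum. If pembrolizumab is given once the reaction settles and the patient stays 21 days, both rules call the patient evaluable. Section 6.0 also defines the combination interventions as both drugs, so the second route in 4.1.1.3 is best read as requiring that all treatment stop. This objection stands and limits the case to patients whose treatment is abandoned before pembrolizumab.

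**It is probably rare.** The monotherapy DLT list has no infusion-reaction exemption, so a related Grade 3 reaction in the window would have been a DLT. Section 2.3 reports no DLTs in escalation through 560 mg. By design that is at least 4 × 1 + 7 × 3 = 25 patients. The upper 95% limit for 0/25 is 1 − 0.05^(1/25) = 11.3%, so rates of 1% to 5% are not excluded, but nothing suggests a common event.

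**There are safeguards.** Under 4.1.1 and 4.1.1.1 the CRC reviews all available data and may ask for further evaluation at a dose. Section 4.1.1.6 has the recommended dose take account of discontinuations that are not DLTs. The patient's events stay in the Safety Population. The CRC Charter, which is not among the documents, may settle evaluability. These points reduce the harm; they do not reconcile the two definitions.

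**The 17% in Section 4.5.** A reader might note that 1/6 is 16.7% and 1/5 is 20%, on either side of that figure. Section 4.5 offers it as a reason for choosing the 3+3, not as a threshold for a reported incidence, and both upper limits in step 2 far exceed it. No weight should be put on the contrast.

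**Conclusion.** The point stands as a conflict between two definitions of the same term, one driving escalation and replacement and the other driving a reported primary endpoint. Followed as written, they permit a combination dose to be cleared partly on a patient never exposed to the combination, and they then produce a reported denominator that does not match the decision.

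The size is one patient in one cohort denominator when it happens. Given one such patient among the first three and an assumed 25% DLT rate, P(clear) goes from 0.60 to at most 0.72. Averaged over assumed frequencies of 1% to 5%, the shift is at most about 0.5 to 2.7 points. Both the DLT rate and the frequencies are assumptions.

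A reader might also infer that a DLT could be lost from the escalation count. The documents do not show that, because Table 6 counts patients with a DLT. Nor is this a general monotherapy problem: a patient who stops for a non-DLT event but stays on study for 21 days is evaluable under both rules. The inconsistency merits correction, but it does not undermine the escalation design.

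**What to change.** Use one definition in Protocol 4.1.1.3, the Synopsis, Protocol 9.3 and SAP 4.3, and have 7.4 refer to it. A patient is evaluable if a DLT occurred in the 21-day window, or if the patient received at least one dose of all assigned study drugs and was followed for 21 days. Everyone else is replaced, and their toxicity is still reviewed by the CRC. If the CRC Charter carries its own rule, align it too.

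The cost is wording in two documents, an occasional replacement patient under a mechanism that 7.4 already provides, and a slightly longer cohort when that happens.

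As a separate, minor consistency edit, Section 6.9.3 treats a required FPT155 dose reduction in the DLT period as a DLT, but the DLT lists in 4.1.1.3, the Synopsis and SAP 2.2.1 omit it. Add it there.

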**Objectives and Endpoints – Phase 1a Dose Escalation/Exploration – FPT155 + Pembrolizumab:**

Objectives	Endpoints
Primary	

 
To evaluate the safety and tolerability of FPT155 in combination with pembrolizumab in patients with advanced non-small cell lung cancer
 
To determine the RD of FPT155 in combination with pembrolizumab in patients with advanced non-small cell lung cancer.
 
	
 
The incidence of adverse events (AEs), serious adverse events (SAEs), clinical laboratory abnormalities, and electrocardiogram (ECG) abnormalities
 
The incidence of dose limiting toxicities (DLTs)
 

Secondary	

 
To evaluate the preliminary clinical response rate of FPT155 in combination with pembrolizumab in patients with non-small cell lung cancer
 
	
 
Objective Response Rate (ORR), defined as the total number of patients with responses of either CR or PR, as determined by the investigator per RECIST v1.1, divided by the total number of patients who are evaluable for a response
 

Exploratory	

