**Table 6: Algorithm for 3+3 Dose Escalation Decisions**

Number of Patients with DLT at a Given Dose Level	Dose Escalation Decision Rule
0/3 or 1/6	Enroll 3 patients at next dose level (next/higher cohort)
1/3	Enroll 3 additional patients at current dose level (current cohort)
$\geq 2$	Stop enrollment. If at the starting dose level, the study will be stopped. If at any other dose level, enroll 3 more patients at the previous dose level (previous/lower cohort) if only 3 were previously enrolled, or at an intermediate dose level

Abbreviations: DLT = dose limiting toxicity.

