#### 4.1.4 Phase 1a FPT155+Pembrolizumab Dose Escalation

FPT155 will start at a dose level a minimum of 2 levels below that cleared in dose escalation with FPT155 monotherapy.

Dose escalation decisions will follow the standard 3+3 algorithm described above and continue up to the dose level established as the MTD for FPT155 monotherapy. Additional intermediate dose levels or dose regimens may be considered upon review of emerging safety, PK and PD results.

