#### 4.5 Scientific Rationale for Study Design

The study is designed as an initial accelerated titration followed by a standard 3+3 dose escalation. The initial accelerated titration component may reduce the number of patients receiving potentially subtherapeutic doses of the study drug. The 3+3 design is chosen to avoid selection of a Phase 2 clinical trial dose that causes a treatment-limiting toxicity in more than 17% of patients, which is a standard that has been considered acceptable as an outpatient therapeutic for patients with limited options and life-threatening disease. This design has the advantage of being rule-based, allocates the lowest dose level to the first cohort, and adaptively escalates/de-escalates based on observed DLTs. Its execution is straightforward and generally well understood by clinicians and investigators, decreasing the potential for deviations from protocol.

Phase 1a dose exploration with mandatory pre- and on-treatment biopsies at doses  $\leq$  MTD will provide additional insight into the safety, PK, PD and mechanism of action of FPT155 and may help in determining the RD for Phase 1b.

Phase 1b for FPT155 monotherapy includes up to 8 tumor-specific cohorts. Patients with advanced RCC and melanoma that have failed prior anti-PD(L)1 therapy will be enrolled in 2 of the 8 cohorts. These patients have a poor prognosis and enrolling them will enable evaluation of the clinical activity of FPT155 in these typically immune-competent tumors that have progressed on a checkpoint inhibitor. Additional tumor types for the remaining 6 Phase 1b cohorts ([Appendix 11](#)) will be determined based on emerging safety, translational, and clinical data for FPT155, as well as any potential new safety signals from other immunotherapies, such as significant changes to prescribing information for approved immunotherapies.

Combination dose escalation with FPT155 and pembrolizumab will start with a FPT155 dose that is a minimum of two dose levels lower than the highest dose cleared during evaluation of FPT155 monotherapy as outlined below in [Table 8](#). Additional patients may be added in combination dose exploration at one or more dose levels that are cleared during combination dose escalation to better characterize the safety profile and preliminary clinical activity. The combination will be limited to patients with non-small cell lung cancer to maximize on the ability to interpret results from the limited enrollment that is planned.

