6.3.1.3 Relationship of Adverse Event to Study Drug

A treatment related AE is an AE noted as related to FPT155 or pembrolizumab by the investigator. Events for which the investigator did not record relationship to study drug will be considered related to study drug for summary purposes. However, by-subject data listings will show the relationship as missing.

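### In the combination cohorts, an event attributed to pembrolizumab and not to FPT155 falls outside the DLT count that drives 3+3 escalation, and the evaluability rules disagree on how to treat that patient

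*Protocol*

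**What the plan says.** Protocol 4.1.1.3, the synopsis and SAP 2.2.1 carry the same opening rule: "DLTs during Phase 1a dose escalation are defined as any of the following deemed by the investigator as related to FPT155". It covers Phase 1a escalation without separating monotherapy from combination. SAP 2.2.1 sits under a monotherapy heading; SAP 2.2.4, on combination escalation, gives no DLT definition of its own.

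The combination subsection of 4.1.1.3, also in the synopsis, works in one direction: "the first occurrence of the following irAEs will not be considered a DLT because they may occur with immune therapy". It then lists exclusions. It does not say whether relatedness to pembrolizumab, or to the combination, qualifies an event.

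For combination escalation, Protocol 4.1.4 states: "Dose escalation decisions will follow the standard 3+3 algorithm described above". A primary objective of that part is "To determine the RD of FPT155 in combination with pembrolizumab", and DLT incidence is a primary endpoint.

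For adverse events in general, SAP 6.3.1.3 uses a wider basis: "A treatment related AE is an AE noted as related to FPT155 or pembrolizumab by the investigator".

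On evaluability, 4.1.1.3 keeps a patient who stops treatment early for a drug-related event, without saying which drug. Protocol 9.3 and SAP 4.3 require either 21 days on study after receiving every assigned drug, or a DLT. Protocol 7.4 replaces escalation patients who are unevaluable and refers back to 4.1.1.3.

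**The concern.** The combination part asks how well the two drugs are tolerated together, but its formal count is limited to events the investigator links to one of them. The protocol itself expects immune-related events from the combination, and both drugs are given on the same day. Appendix 2 tells investigators that a relationship needs supporting evidence, that concomitant therapy is an alternative cause to consider, and that product information should be consulted for marketed products. Under that guidance, a recognised pembrolizumab toxicity could be attributed to pembrolizumab alone.

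Any such event lowers the counted rate below the rate patients experience, and each level becomes easier to clear. The MTD is read from this count, and 4.1.1.6 makes the MTD an upper limit for the recommended dose. An undercount therefore loosens the one fixed cap in the scheme.

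**Working it through.** **The plan's own figure.** Protocol 4.5 gives the purpose of the escalation scheme: "avoid selection of a Phase 2 clinical trial dose that causes a treatment-limiting toxicity in more than 17% of patients". This matches the escalation boundary in Table 6: 1/6 = 16.7%, rounded to 17%. The statement concerns toxicity in patients and names no drug.

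**Inputs.** Table 6 escalates on 0/3 or 1/6 and stops at 2 or more. The true rate p of DLT-criterion toxicity, and the share f of those events attributed to pembrolizumab and not to FPT155, are not in the documents. Both are assumed here: f = 10%, 25%, 50%, and several values of p.

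**Formulas.** If the affected patient stays in the cohort, the counted rate is q = p(1 − f). The chance that a level clears is

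P(clear) = (1 − q)³ + 3q(1 − q)² × (1 − q)³.

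**Worked case, p = 1/3.**
- All events counted, q = 1/3: 0.296 + 0.132 = 0.43.
- f = 10%, q = 0.30: 0.343 + 0.151 = 0.49.
- f = 25%, q = 0.25: 0.422 + 0.178 = 0.60.
- f = 50%, q = 1/6: 0.579 + 0.201 = 0.78.

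**Other true rates.**

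| True rate p | All counted | f = 10% | f = 25% | f = 50% |
|---|---|---|---|---|
| 1/6 | 0.78 | 0.81 | 0.86 | 0.93 |
| 0.30 | 0.49 | 0.56 | 0.65 | 0.81 |
| 1/3 | 0.43 | 0.49 | 0.60 | 0.78 |
| 0.40 | 0.31 | 0.38 | 0.49 | 0.71 |
| 0.50 | 0.17 | 0.23 | 0.35 | 0.60 |

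At f = 50%, a level with true rate 1/3 clears as often (0.78) as a level at the 17% boundary would with every event counted.

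**If the patient leaves and is replaced.** The counted rate becomes q = p(1 − f)/(1 − pf). At p = 1/3 this is 0.310, 0.273 or 0.200, and P(clear) is 0.47, 0.55 or 0.71. Clearance is inflated slightly less, but the event disappears from both numerator and denominator.

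**Evaluability, side by side.** Take a patient who stops treatment and leaves the study on day 12 after a severe event attributed to pembrolizumab alone.
- Under 4.1.1.3 the patient is evaluable, if a pembrolizumab-related event is read as drug-related.
- Under Protocol 9.3 and SAP 4.3 the patient has neither completed 21 days nor had a counted DLT, so is outside the population used for the DLT tables.
- Whether 7.4 leads to replacement depends on which definition is applied.

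**The case against.** The strongest reply is that few events may be affected. An event judged related to both drugs is related to FPT155 and counts. Same-day dosing and a 21-day window make joint attribution plausible. The combination exclusions also remove, whatever the attribution, several event types for which timing might have separated the drugs, such as transient Grade 3 infusion reactions. At f = 10% and a true rate of 1/6, the chance of clearing moves only from 0.78 to 0.81. This stands: the size is unknown and could be small.

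A reader might infer that pembrolizumab toxicity is ignored when the combination dose is chosen. The documents do not support that. Under 4.1.1.6 the recommended dose draws on all safety, tolerability, PK and PD data, including toxicity that does not meet DLT criteria. Under 4.1.1.1 the review committee sees emerging and cumulative safety data. The combination subsection allows escalation to be paused on safety grounds. Under 6.9.3 an FPT155 dose reduction in the DLT period is a DLT with no attribution test stated. SAP 6.3.1.6 tabulates Grade 3 or higher events regardless of cause, and pembrolizumab-related events separately. These safeguards limit the harm, but they are matters of judgement or reporting and do not change the 3+3 count.

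A reader might also infer that the DLT table and the related-event tables rest on different bases. That is too strong. The related-event tables in SAP 6.3.1.6 are per drug, and the FPT155 one matches the DLT rule. The mismatch is only with the general definition in SAP 6.3.1.3.

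Finally, an extra table does not alter escalation, whose process is set in the committee's charter. That is true, so the wording must be reconciled as well.

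**Conclusion.** The point holds, in a limited form. As written, events attributed to pembrolizumab and not to FPT155 are outside the 3+3 count, the MTD and the primary DLT endpoint for the combination, and no other section found brings them back. The direction is certain: any share above zero makes clearance easier. The size is not. The shares of 10% to 50% are assumptions, and at a true rate of 1/3 they move the chance of clearing from 0.43 to between 0.49 and 0.78. The calculation also assumes independent patients and strict use of Table 6.

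The conflict between 4.1.1.3 and 9.3 on evaluability needs no assumed share, although it depends on whether drug-related in 4.1.1.3 includes pembrolizumab. It needs settling in any case. Both matters should be corrected, but neither shows that the combination dose would be wrongly chosen.

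**What to change.** 1. Reconcile, for the combination cohorts, which drug relationship qualifies an event as a DLT. The places are the synopsis DLT definition and its combination considerations, Protocol 4.1.1.3 and its combination subsection, and SAP 2.2.1, 2.2.4 and 6.3.1.3. The choice of clinical rule is the sponsor's; this review proposes none.
2. Reconcile the evaluability wording in 4.1.1.3 with Protocol 9.3 and SAP 4.3, so that 7.4 has a single reading for a patient who leaves early after a pembrolizumab-attributed event.
3. In SAP 6.3.1.7, for combination escalation, tabulate DLT-criterion events within 21 days on two bases: related to FPT155, and related to either drug. Apply the same combination exclusions to both, so that only attribution differs. Present this for the DLT-Evaluable Population and for all treated combination-escalation patients. Restricted to the first, the table could miss the very patients at issue.

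SAP 6.3.1.6 already plans summaries by relatedness to each drug, so the attribution data are expected to exist. The cost is wording changes, one extra tabulation and possibly less favourable counts.
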